6.1.1 Exclusions to Routine Adverse Event Recording

There are no exclusions to routine adverse event reporting/recording for this protocol.

6.2 DATA SHARING PLANS

6.2.1 Human Data Sharing Plan

De-identified human data generated for use in future and ongoing research will be shared through a NIH-funded or approved repository (ClinicalTrials.gov) and BTRIS. At the completion of data analysis, data will be submitted to ClinicalTrials.gov either before publication or at the time of publication or shortly thereafter. Data may also be used to support long-term research efforts within the NCI SB and de-identified data may also be shared with collaborators as specified in protocol 03-C-0277.

6.2.2 Genomic Data Sharing Plan

The NIH Genomic Data Sharing Policy does not apply to this study.

6.3 RESPONSE CRITERIA

For the purposes of this study, patients should be re-evaluated for response approximately two weeks following the last vaccination, then one month later x1, and then every 1-2 months for the first year, and then annually or as clinically indicated. In addition to a baseline scan, confirmatory scans should also be obtained at least 4 weeks following initial documentation of objective response.

Response and progression will be evaluated in this study using the new international criteria proposed by the revised Response Evaluation Criteria in Solid Tumors (RECIST) guideline (version 1.1)¹⁸. Changes in the largest diameter (unidimensional measurement) of the tumor lesions and the shortest diameter in the case of malignant lymph nodes are used in the RECIST criteria.

6.3.1 Definitions

Evaluable for toxicity: All patients will be evaluable for toxicity from the time of their first treatment with peptide loaded dendritic cell vaccine.

Evaluable for objective response: Only those patients who have measurable disease present at baseline, have received at least one cycle of therapy, and have had their disease re-evaluated will be considered evaluable for response. These patients will have their response classified according to the definitions stated below. (Note: Patients who exhibit objective disease progression prior to the end of cycle 1 will also be considered evaluable.)

Evaluable Non-Target Disease Response: Patients who have lesions present at baseline that are evaluable but do not meet the definitions of measurable disease, have received at least one cycle of therapy, and have had their disease re-evaluated will be considered evaluable for non-target disease. The response assessment is based on the presence, absence, or unequivocal progression of the lesions.

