3.1.2 Treatment Phase

The protocol will consist of two cohorts: cohort 1, patients with melanoma and cohort 2, patients with epithelial cancer.

The study will utilize an optimal design where initially 21 evaluable patients will be enrolled to each cohort. If 0 or 1 of the 21 patients in a given cohort experiences a clinical response, then no further patients will be enrolled; if 2 or more of the first 21 evaluable patients enrolled have a clinical response, then accrual will continue until a total of 41 evaluable patients have been enrolled to that cohort.

Patients will receive no other experimental agents while on this protocol. All patients will receive one course of treatment (4 vaccination cycles). The start date of the course will be the start date of the first vaccination; the end date will be the day of the first post-treatment evaluation (week 8 if the patient receives all 4 cycles).

Enrollment will be staggered within each cohort with three weeks between start dates for the first three patients to allow for a 3-week interval for safety assessment before the next enrolled patient is scheduled to receive their first dose of the DC vaccine.

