3.4 POST-TREATMENT EVALUATION (FOLLOW-UP)

3.4.1 1st Follow-up Evaluation (Day 56 \pm 5 days)

All patients will return to the NIH Clinical Center for their first follow-up evaluation on day 56 (\pm 5 days), which is approximately 2 weeks from the 4th vaccination.

At the first follow-up evaluation, patients will undergo:

- Physical examination, including ECOG
- Vital signs
- CBC w/differential
- Acute Care Panel (sodium, potassium, chloride, bicarbonate, creatinine, glucose, BUN), Hepatic Panel (alkaline phosphatase, AST, ALT, total bilirubin, direct bilirubin), Mineral Panel (albumin, calcium, magnesium, phosphorus), Uric Acid, Creatinine Kinase, Lactate Dehydrogenase, Total Protein
- Lymphocyte phenotyping (TBNK)
- β -HCG pregnancy test (serum or urine) on all females of child-bearing potential
- Toxicity assessment, including a review of systems
- Research samples as described in Section **5**
- Imaging studies as performed at baseline to determine tumor response. If clinically indicated, other scans or x-rays may be performed, e.g., brain MRI, bone scan.
- A 5-liter leukapheresis may be performed. If the patient is unable to undergo leukapheresis, approximately 96 mL of blood may be obtained. This will be conducted under 03-C-0277.

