3.4.2 Subsequent Follow-up Evaluations

The second follow-up evaluation will take place 1 month (\pm 5 days) after the first follow-up evaluation (Day 56). Subsequent follow-up evaluations will take place every 1-2 months for the first year, and then annually or as clinically appropriate as determined by the PI. As noted in Section **3.4.1**, additional leukapheresis may be performed only at the first follow-up evaluation. It will not be performed at any other post-treatment evaluations.

Note: Patients may be seen more frequently as clinically indicated.

At each scheduled follow-up evaluation, patients will undergo:

- Physical examination, including ECOG
- Vital signs
- CBC w/differential
- Acute Care Panel (sodium, potassium, chloride, bicarbonate, creatinine, glucose, BUN), Hepatic Panel (alkaline phosphatase, AST, ALT, total bilirubin, direct bilirubin), Mineral Panel (albumin, calcium, magnesium, phosphorus), Uric Acid, Creatinine Kinase, Lactate Dehydrogenase, Total Protein
- Lymphocyte phenotyping (TBNK)
- β -HCG pregnancy test (serum or urine) on all females of child-bearing potential (complete at all follow-up evaluations within 4 months after the last vaccine)
- Toxicity assessment, including a review of systems
- Research samples as described in Section **5**
- Imaging studies as performed at baseline to determine tumor response. If clinically indicated, other scans or x-rays may be performed, e.g., brain MRI, bone scan.

Note: Patients who are unable or unwilling to return for follow-up evaluations may be followed via phone or e-mail contact. Patients may be asked to send laboratory, imaging and physician exam reports performed by their treating physician.

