8 STATISTICAL CONSIDERATIONS

8.1 STATISTICAL HYPOTHESIS

8.1.1 Primary Efficacy Endpoint

The primary objectives of this trial is to determine the clinical response rate in patients with metastatic melanoma or epithelial cancers who receive this dendritic cell vaccine.

The objective response rate (responses/evaluable patients) is the measurable endpoint, and it will be of interest to determine if it exceeds 10% and is consistent with 25%.

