8.2 SAMPLE SIZE DETERMINATION

Assays to assess quality and quantity of the vaccine induced cells will include Eliza and Elispot assays assessing reactivity to the mutated peptide compared to the non-mutated peptide. Patients will be enrolled into 2 individual cohorts; melanoma and common epithelial cancers. For each of the 2 cohorts, the study will be conducted using a phase II optimal design¹⁹ (Simon R, Controlled Clinical Trials 10:1-10, 1989). The objective will be to determine if the vaccine is able to be associated with a clinical response rate that can rule out 5% ($p_0=0.05$) in favor of a modest 20% PR + CR rate ($p_1=0.20$).

In patients in each of the two cohorts, the following design will be used. For each cohort, with $\alpha=0.05$ (5% probability of accepting a poor therapy) and $\beta=0.10$ (10% probability of rejecting a good therapy,), initially 21 evaluable patients will be enrolled. If 0 or 1 of the 21 patients experiences a clinical response, then no further patients will be enrolled. If 2 or more of the first 21 evaluable patients enrolled have a clinical response, then accrual will continue until a total of 41 evaluable patients have been enrolled. As it may take several weeks to determine if a patient has experienced a clinical response, a temporary pause of up to 6 months in the accrual to the trial may be necessary to ensure that enrollment to the second stage is warranted. If 2 to 4 of the 41 have a clinical response, then this will be considered inadequate for further investigation. If 5 or more of 41 patients have a clinical response, then this will indicate that this strategy provides a new approach that may be worthy of further consideration. Under the null hypothesis (5% response rate), the probability of early termination is 72%.

A total of up to 86 patients may be required (allowing up to 2 inevaluable patients per cohort). Provided that about 1-2 patients per month will be able to be enrolled onto this trial, approximately 6 years may be needed to accrue the maximum number of required patients.

However, as adequate responses to proceed to the second stage of accrual may not occur, the trial may end up accruing as few as 21 patients in each cohort.

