8.3 POPULATION FOR ANALYSES

Modified intention to treat analysis dataset. Patients who receive adequate treatment (defined as the administration of peptide pulsed antigen presenting cells) will be considered evaluable and included in the statistical analyses

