8.4.2 Analysis of the Primary Endpoints

For each cohort, the clinical response rate (PR+CR/number of evaluable subjects) will be determined and reported along with the corresponding 95% two-sided confidence interval.

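### Sections 6.3.1 and 8.3 conflict on whether a vaccinated patient with no disease re-evaluation is evaluable, and the stage rule and response-rate denominator do not say which applies

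*Combined protocol and SAP*

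**What the plan says.** Two sections define who is evaluable.

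- **Section 6.3.1**, under its label for objective response, limits evaluability to patients with measurable baseline disease who "have received at least one cycle of therapy, and have had their disease re-evaluated will be considered evaluable for response". The sentence opens with the word only. Its one exception is objective progression before the end of cycle 1, which also counts as evaluable.
- **Section 8.3**, the analysis population, describes a modified intention-to-treat set. Patients with adequate treatment, "defined as the administration of peptide pulsed antigen presenting cells) will be considered evaluable and included in the statistical analyses". It has no re-evaluation condition.

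Four places depend on the word and cite neither definition.

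- Section 3.1.2: accrual continues "if 2 or more of the first 21 evaluable patients enrolled have a clinical response". Section 8.2 repeats the rule and the total of 41 evaluable patients per cohort.
- Section 8.1.1: "The objective response rate (responses/evaluable patients) is the measurable endpoint".
- Section 8.4.2: for each cohort, "the clinical response rate (PR+CR/number of evaluable subjects) will be determined", with a 95% two-sided confidence interval.
- Section 8.2: "A total of up to 86 patients may be required (allowing up to 2 inevaluable patients per cohort". It does not say what makes a patient inevaluable.

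Section 8.4.6, on the interim look, refers only to 8.2.

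**The concern.** The conflict concerns one group: vaccinated patients with neither a disease re-evaluation nor documented objective progression. The other conditions in 6.3.1 do not separate the two sections, because measurable disease is an inclusion criterion (2.1.1) and one vaccine is one cycle (3.5).

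These patients cannot be recorded as responders. Under 8.3 they stay in the denominator and count against the vaccine. Under 6.3.1 they leave it, and further patients are enrolled until 21 or 41 evaluable patients are reached. The primary endpoint and the decision to continue past stage 1 therefore depend on which section is applied. Because the trial is open and single-arm, that choice could be made after responses are known.

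The group need not be empty. Patients are refractory to standard therapy with ECOG up to 2 (2.1.1). The first scheduled post-vaccine imaging is at Day 56 (3.4.1). Death, withdrawal and loss to follow-up take a patient off study, after which no data can be collected (3.6.2). Section 6.3.4.3 itself provides for symptomatic deterioration without objective progression.

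**Working it through.** **Inputs.** From 8.2: p0 = 0.05, p1 = 0.20; stop if 0 or 1 of 21 respond; success if 5 or more of 41 respond. (Section 8.1.1 mentions 10% and 25%; the 8.2 pair is used because the design is built on it.) The share d of vaccinated patients never re-evaluated is not in the documents. It is an assumption, shown at 0, 2/43 (4.7%, numerically the plan's allowance of 2 in 43), 10% and 20%.

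**Step 1: reproduce the plan.** With b(x; n, p) the binomial probability:

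- P(stop at stage 1) = b(0; 21, p) + b(1; 21, p). At p = 0.05 this is 0.3406 + 0.3764 = 0.717; the plan states 72%.
- P(success) = sum over x = 2 to 21 of b(x; 21, p) × P(Bin(20, p) ≥ 5 − x). This gives 0.046 at p = 0.05 and 0.902 at p = 0.20.
- Total: 2 × (41 + 2) = 86, as stated.

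The design figures are correct. They are also the operating characteristics under 8.3 when the response rate refers to all vaccinated patients, whatever d is.

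**Step 2: the same rule under 6.3.1.** If a share p of all vaccinated patients respond and a share d are never re-evaluated (none of them recorded responders), each evaluable patient responds with probability p/(1 − d). With dropped patients replaced until 21 and then 41 are evaluable, the Step 1 formulas apply at that rate.

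| d | 0.05/(1 − d) | P(continue past stage 1) | P(success), true 5% | P(success), true 20% |
|---|---|---|---|---|
| 0 | 0.0500 | 0.283 | 0.046 | 0.902 |
| 2/43 | 0.0524 | 0.302 | 0.054 | 0.922 |
| 10% | 0.0556 | 0.327 | 0.066 | 0.943 |
| 20% | 0.0625 | 0.381 | 0.097 | 0.973 |

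The continuation column is at a true 5%. Reaching 41 evaluable patients takes on average 41/(1 − d) vaccinated: 43.0 at d = 2/43, 45.6 at 10% and 51.3 at 20%. The last two exceed the 43 per cohort foreseen in 8.2, which does not say what happens then; those rows assume replacement continues.

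**Step 3: one fixed set of patients.** Take 41 vaccinated, 5 responders and 2 never re-evaluated. Under 8.3 the rate is 5/41 = 12.2% (exact 95% CI 4.1 to 26.2%). Dropping the two without replacement gives 5/39 = 12.8% (4.3 to 27.4%).

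**Step 4: the stage-1 boundary.** Take 21 vaccinated, 1 responder and 2 never re-evaluated. Under 8.3 the cohort stops. Under 6.3.1 there are 19 evaluable patients and two more are sought. With a true 5% rate and d = 2/43, the chance that at least one of those two responds is 1 − (1 − 0.0524)² = 10.2%.

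**Step 5: the power cost of 8.3 if the 20% target was meant for re-evaluated patients only.** The rate in all vaccinated patients is then 0.20 × (1 − d): 0.191, 0.180 and 0.160 at d = 2/43, 10% and 20%. Power is 0.878, 0.844 and 0.760.

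**The case against.** The strongest reply is that 8.3 already governs. It is headed as the analysis population, stands in the same chapter as the hypothesis, sample size and primary analysis, and defines the unqualified word those sections use. Section 6.3.1 defines labelled categories for classifying response. On that reading only a cross-reference is missing. Most of this stands, and 8.3 is the more natural reading. It does not settle the matter, because 8.1.1 calls the endpoint an objective response rate over evaluable patients, the only definition carrying that label is in 6.3.1, and that definition is exclusive. No text sets precedence.

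The affected group is also limited. Early objective progression stays evaluable. Day 56 includes, for all patients, "Imaging studies as performed at baseline to determine tumor response". For those who do not return, "Patients may be asked to send laboratory, imaging and physician exam reports performed by their treating physician". Section 6.3.4.3 asks for every effort to document progression. These provisions make d smaller but do not make it zero.

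A reader might infer three stronger points that the documents do not support.

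- **That 6.3.1 always inflates the reported rate.** This holds only for a fixed set of patients. With replacement, the realised rate can move either way; it is the expected rate that rises.
- **That power collapses if a cohort reaches 43 vaccinated with fewer than 41 evaluable.** This needs a rule voiding success below 41 evaluable. Section 8.2 says only that up to 86 may be required and contains no such rule.
- **That the allowance of 2 covers only enrolled patients never vaccinated.** This is possible, since patients enrol before the first vaccine and leave the study if cells fail release testing (2.3.1, 3.6.2), but 8.2 does not say so.

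**Conclusion.** The conflict is real, and it affects the denominator of the primary endpoint and the stage-1 decision. Under 8.3 there is no bias and the design performs as stated. Under 6.3.1 as written, the expected response rate rises and the false-positive probability passes the planned 0.05 at each non-zero d examined. At d = 2/43 the changes are small: under one percentage point in false-positive probability and about two in the chance of continuing. They become material only if 10% to 20% of vaccinated patients go unassessed.

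These figures rest on an assumed d, independent patients and unrestricted replacement. The consequence is bounded, because analyses are descriptive (8.4.1) and success means only that the approach may merit further consideration (8.2). The sample size itself is not in error. This should be fixed, because a rule that can add 20 evaluable patients to a cohort should not turn on an unresolved definition.

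**What to change.** - In 3.1.2, 8.1.1, 8.2 and 8.4.2, with a cross-reference in 6.3.1, state that the stage-1, final and confidence-interval denominators are the 8.3 population: all patients given at least one vaccine.
- Count vaccinated patients with no post-baseline disease assessment as non-responders, including those with symptomatic deterioration and no assessment.
- Report the 6.3.1 re-evaluated-only rate as a supporting result.
- Reword the allowance of 2 inevaluable patients per cohort in 8.2 so that it is consistent with this definition.

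The cost is wording only, with no added visits and no change to the 21 and 41. The reported rate may be slightly lower than under 6.3.1. If the 20% target was meant for re-evaluated patients only, the loss of power in Step 5 should be stated in 8.2; if it was meant for all vaccinated patients, power stays at 0.902.

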6.3.2 Disease Parameters

Measurable disease: Measurable lesions are defined as those that can be accurately measured in at least one dimension (longest diameter to be recorded) as:

- By chest x-ray: ≥ 20 mm;
- By CT scan:
 - Scan slice thickness 5 mm or under: ≥ 10 mm
 - Scan slice thickness > 5 mm: double the slice thickness
- With calipers on clinical exam: ≥ 10 mm.

All tumor measurements must be recorded in millimeters (or decimal fractions of centimeters).

Note: Tumor lesions that are situated in a previously irradiated area might or might not be considered measurable. If the investigator thinks it appropriate to include them, the conditions under which such lesions should be considered must be defined in the protocol.

Malignant lymph nodes: To be considered pathologically enlarged and measurable, a lymph node must be >15 mm in short axis when assessed by CT scan (CT scan slice thickness recommended to be no greater than 5 mm). At baseline and in follow-up, only the short axis will be measured and followed.

Non-measurable disease: All other lesions (or sites of disease), including small lesions (longest diameter <10 mm or pathological lymph nodes with ≥ 10 to <15 mm short axis), are considered non-measurable disease. Bone lesions, leptomeningeal disease, ascites, pleural/pericardial effusions, lymphangitis cutis/pulmonitis, inflammatory breast disease, and abdominal masses (not followed by CT or MRI), are considered as non-measurable.

Target lesions: All measurable lesions up to a maximum of 2 lesions per organ and 5 lesions in total, representative of all involved organs, should be identified as target lesions and recorded and measured at baseline. Target lesions should be selected on the basis of their size (lesions with the longest diameter), be representative of all involved organs, but in addition should be those that lend themselves to reproducible repeated measurements. It may be the case that, on occasion, the largest lesion does not lend itself to reproducible measurement in which circumstance the next largest lesion which can be measured reproducibly should be selected. A sum of the diameters (longest for non-nodal lesions, short axis for nodal lesions) for all target lesions will be calculated and reported as the baseline sum diameters. If lymph nodes are to be included in the sum, then only the short axis is added into the sum. The baseline sum diameters

will be used as reference to further characterize any objective tumor regression in the measurable dimension of the disease.

Non-target lesions: All other lesions (or sites of disease) including any measurable lesions over and above the 5 target lesions should be identified as non-target lesions and should also be recorded at baseline. Measurements of these lesions are not required, but the presence, absence, or in rare cases unequivocal progression of each should be noted throughout follow-up.

6.3.3 Methods for Evaluation of Measurable Disease

All measurements should be taken and recorded in metric notation using a ruler or calipers. All baseline evaluations should be performed as closely as possible to the beginning of treatment and never more than 4 weeks before the beginning of the treatment.

The same method of assessment and the same technique should be used to characterize each identified and reported lesion at baseline and during follow-up. Imaging-based evaluation is preferred to evaluation by clinical examination unless the lesion(s) being followed cannot be imaged but are assessable by clinical exam.

Clinical lesions: Clinical lesions will only be considered measurable when they are superficial (e.g., skin nodules and palpable lymph nodes) and ≥ 10 mm diameter as assessed using calipers (e.g., skin nodules). In the case of skin lesions, documentation by color photography, including a ruler to estimate the size of the lesion, is recommended.

Conventional CT and MRI: This guideline has defined measurability of lesions on CT scan based on the assumption that CT slice thickness is 5 mm or less. If CT scans have slice thickness greater than 5 mm, the minimum size for a measurable lesion should be twice the slice thickness. MRI is also acceptable in certain situations (e.g. for body scans). Ideally, the same type of scanner should be used and the image acquisition protocol should be followed as closely as possible to prior scans. Body scans should be performed with breath-hold scanning techniques, if possible.

FDG-PET: While FDG-PET response assessments need additional study, it is sometimes reasonable to incorporate the use of FDG-PET scanning to complement CT scanning in assessment of progression (particularly possible 'new' disease). New lesions on the basis of FDG-PET imaging can be identified according to the following algorithm:

- Negative FDG-PET at baseline, with a positive FDG-PET at follow-up is a sign of PD based on a new lesion.
- No FDG-PET at baseline and a positive FDG-PET at follow-up: If the positive FDG-PET at follow-up corresponds to a new site of disease confirmed by CT, this is PD. If the positive FDG-PET at follow-up is not confirmed as a new site of disease on CT, additional follow-up CT scans are needed to determine if there is truly progression occurring at that site (if so, the date of PD will be the date of the initial abnormal FDG-PET scan). If the positive FDG-PET at follow-up corresponds to a pre-existing site of disease on CT that is not progressing on the basis of the anatomic images, this is not PD.
- FDG-PET may be used to upgrade a response to a CR in a manner similar to a biopsy in cases where a residual radiographic abnormality is thought to represent fibrosis or scarring. The use of FDG-PET in this circumstance should be prospectively described in the protocol and supported by disease-specific medical literature for the indication.

However, it must be acknowledged that both approaches may lead to false positive CR due to limitations of FDG-PET and biopsy resolution/sensitivity.

Note: A ‘positive’ FDG-PET scan lesion means one which is FDG avid with an uptake greater than twice that of the surrounding tissue on the attenuation corrected image.

